10.4. Ethical Conduct of the Study

The study will be conducted in accordance with legal and regulatory requirements, as well as with scientific purpose, value, and rigor and follow generally accepted research practices described in Guidelines for Good Epidemiologic Practice and Best Practices for Conducting, Reporting Pharmacoepidemiologic Safety Studies Using Electronic Healthcare Data Sets, and the IPSE GPP.

11. MANAGEMENT AND REPORTING OF ADVERSE EVENTS/ADVERSE REACTIONS

This study involves data that exist as structured data by the time of study start. In these data sources, individual patient data are not retrieved or validated, and it is not possible to link (i.e., identify a potential association between) a particular product and medical event for any individual. Thus, the minimum criteria for reporting an adverse event (AE) (i.e., identifiable patient, identifiable reporter, a suspect product, and event) cannot be met.

12. PLANS FOR DISSEMINATING AND COMMUNICATING STUDY RESULTS

Study results will be summarized in an interim study report inclusive of the primary objective and exploratory objectives 1 through 3. The interim study report and final study are planned to be provided to the FDA and EMA. Both the interim and final study reports will be disseminated to all the relevant members internally. The study is registered in the HMA EMA Catalogue.

Study results, separately by dataset, will be communicated, presented, and/or published in scientific journals or other scholarly media.

Authorship of study manuscripts and presentations at scientific conferences will follow the guidelines established by the International Committee of Medical Journal Editors (https://www.icmje.org/).

In the event of any prohibition or restriction imposed (e.g., clinical hold) by an applicable competent authority in any area of the world, or if the party responsible for collecting data from the participant is aware of any new information which might influence the evaluation of the benefits and risks of a Pfizer product, Pfizer should be informed immediately.

ANNEX 1. LIST OF STANDALONE DOCUMENTS

Number	Document Reference Number	Date	Title
001		23	Pfizer SCD KRD+ Data Dictionary
		December	
		2024	

ANNEX 2. ADDITIONAL INFORMATION

Annex Table 1. Covariate and Outcome Operational Definitions

Code lists will be included in SAP document.

Variables	Operational Definition ¹			
Demographic Variables	Demographic Variables			
Age	Age in years (continuous)			
Sex	Sex (categorical) • Male • Female • Unknown • Missing			

V2.0 23 December 2024		
Race	Race/Ethnicity (categorical) White Black or African American Asian or Pacific Islander Hispanic or Latino Other Missing	
Insurance Type	Insurance (categorical)	
Region	Region, based on Census geographic regions (categorical) Northeast Midwest South West Missing	
Top 10 Diagnosing Provider Specialty	Top 10 provider specialties present on the same claim as a SCD diagnosis • To be determined, pending data explorations	
SCD Hematology Diagnosing Provider	Categorical record of a medical claim with a hematologist provider, assessed as the value present on the same claims as an SCD diagnosis, • Yes • No (includes non-hematology and null values)	
SCD Genotype ¹	Genotype (categorical) • Homozygous SS • HSC • HbSB0 thalassemia • HbSB+ thalassemia • Unknown/Other	
SCD Comorbidities		
Acute Chest Syndrome	Presence of an ICD-10-Clinical Modification (CM) diagnosis code on any claim	
Acute Chest Syndrome + Pneumonia	Presence of an ICD-10-CM diagnosis code on any claim for the following conditions: Acute chest syndrome,	

V2.0 23 December 2024		
	AND Pneumonia	
Acute Coronary Syndrome	Presence of an ICD-10-CM diagnosis code on any claim	
Acute Osteomyelitis	Presence of an ICD-10-CM diagnosis code on any claim	
Acute Renal Failure	Presence of an ICD-10-CM diagnosis code on any claim	
Aplastic Crisis	Presence of an ICD-10-CM diagnosis code on any claim	
Intracerebral And Subarachnoid Hemorrhage	Presence of an ICD-10-CM diagnosis code on any claim	
Myocardial Infarction	Presence of an ICD-10-CM diagnosis code on any claim	
Priapism	Presence of an ICD-10-CM diagnosis code on any claim	
Splenic Sequestration Crisis	Presence of an ICD-10-CM diagnosis code on any claim	
Transfusion- Associated Reaction	Presence of an ICD-10-CM diagnosis code on any claim	
Vaso-Occlusive Crisis (VOC)	Definition 1 (primary analysis, strict definition): • Presence of ICD-10 diagnoses code for SCD with VOC (D57.09, D57.21, D57.41, D57.43, D57.45, D57.81) or dactylitis (D57.04, D57.214, D57.414, D57.434, D57.454, D57.814) on a claim from one of the following healthcare settings: • Urgent care visit • Emergency visit • Inpatient visit	
	Definition 2 (sensitivity analysis, broad definition): • Presence of ICD-10 diagnoses code for VOCs (definition 1) and/or VOC component (e.g., ACS, priapism, stroke, splenic sequestration, or crisis unspecified) on a claim from one of the following healthcare settings:	

V2.0 23 December 2024	T s	
	 Telemedicine visit Office clinic visit: Outpatient visit Urgent care visit Emergency visit Inpatient visit 	
	Final definition to be included in SAP.	
Venous Thromboembolism	Presence of an ICD-10-CM diagnosis code on any claim	
Avascular Necrosis	Presence of an ICD-10-CM diagnosis code on any claim	
Cholelithiasis	Presence of an ICD-10-CM diagnosis code on any claim	
Chronic Kidney Disease	Presence of an ICD-10-CM diagnosis code on any claim	
Chronic Pain	Presence of an ICD-10-CM diagnosis code on any claim	
Diabetes	Presence of an ICD-10-CM diagnosis code on any claim	
Heart Failure	Presence of an ICD-10-CM diagnosis code on any claim	
Iron Overload	Presence of an ICD-10-CM diagnosis code on any claim	
Leg Ulcer	Presence of an ICD-10-CM diagnosis code on any claim	
Pulmonary Hypertension	Presence of an ICD-10-CM diagnosis code on any claim	
Retinopathy	Presence of an ICD-10-CM diagnosis code on any claim	
Treatments		
Voxelotor	Presence of a national drug code (NDC) or generic name on a pharmacy event claim	

7	12	0	23	D	ecem	her	20	24

1 - 1 - 1 - 1 - 1 - 1 - 1 - 1 - 1 - 1 -	
Hydroxyurea	Presence of a national drug code (NDC) or generic name on a pharmacy event claim
Crizanlizumab	Presence of a national drug code (NDC) or generic name on a pharmacy event claim
	OR
	Presence of an ICD-10-CM procedure, Current Procedural Terminology (CPT), or Healthcare Common Procedure Coding System (HCPCS) code on any claim
L-glutamine	Presence of a national drug code (NDC) or generic name on a pharmacy event claim
Erythropoietin Stimulating Agent	Presence of a national drug code (NDC) or generic name on a pharmacy event claim
(ESA)	OR
	Presence of an ICD-10-CM procedure, Current Procedural Terminology (CPT), or Healthcare Common Procedure Coding System (HCPCS) code on any claim
Other Covariates	
RBC transfusion	Presence of an ICD-10-CM procedure, Current Procedural Terminology (CPT), or Healthcare Common Procedure Coding System (HCPCS) code on any claim
	Multiple codes or claims occurring on the same day will be assessed as a single RBC transfusion event.
Hb lab test	Presence of a LOINC or CPT/HCPCS code,
	OR no presence of a LOINC or CPT/HCPCS code
Hb value	Presence of a LOINC code,
	AND
	A non-missing, numeric lab result value
Healthcare Interactions - Inpatient/Outpatient Visit	Presence of any claim in the following tables:

7	12	0	23	D	ecem	her	2.0	124	Ī

resence of an ICD-10-CM diagnosis code on any claim
resence of a national drug code (NDC) or generic name on a pharmacy vent claim
DR .
Presence of an ICD-10-CM procedure, Current Procedural Terminology CPT), or Healthcare Common Procedure Coding System (HCPCS) code in any claim
resence of an ICD-10-CM diagnosis code on any claim
resence of an ICD-10-CM diagnosis code on any claim
CCI (continuous)
ee SCD comorbidities definition above
resence of an ICD-10-CM diagnosis code on any claim
resence of an ICD-10-CM diagnosis code on any claim
resence of an ICD-10-CM diagnosis code on any claim
resence of an ICD-10-CM diagnosis code on any claim
resence of an ICD-10-CM diagnosis code on any claim
resence of an ICD-10-CM diagnosis code on any claim
resence of an ICD-10-CM diagnosis code on any claim

VZ.0 Z5 December Z0Z1	
Mild Liver Disease	Presence of an ICD-10-CM diagnosis code on any claim
Diabetes Without Chronic Complication	Presence of an ICD-10-CM diagnosis code on any claim
Diabetes With Chronic Complication	Presence of an ICD-10-CM diagnosis code on any claim
Hemiplegia or Paraplegia	Presence of an ICD-10-CM diagnosis code on any claim
Renal Disease (Mild to Moderate)	Presence of an ICD-10-CM diagnosis code on any claim
Renal Disease (Severe)	Presence of an ICD-10-CM diagnosis code on any claim
Any Malignancy Without Metastasis Including Leukemia and Lymphoma	Presence of an ICD-10-CM diagnosis code on any claim
Moderate or Severe Liver Disease	Presence of an ICD-10-CM diagnosis code on any claim
Metastatic Solid Tumor	Presence of an ICD-10-CM diagnosis code on any claim
Human immunodeficiency virus	Presence of an ICD-10-CM diagnosis code on any claim
Acquired Immunodeficiency Syndrome	Presence of an ICD-10-CM diagnosis code on any claim
Patient-Level Outcome I	Definitions
RBC transfusions	For each patient, the number of RBC transfusions will be evaluated PPPY in baseline and follow-up. See covariate definition above for operational definition and Table 5 for output definition. See Annex Table 2 for RBC transfusion codes.
Stroke (including transient ischemic attack)	For each patient, stroke will be evaluated as the time to stroke in days. See covariate definition above for operational definition and Table 5 for output definition.

The Le Broomeer Lear	
VOCs	For each patient, the number of VOCs will be evaluated PPPY in baseline and follow-up.
	See covariate definition above for operational definition and Table 5 for output definition.
ACS	For each patient, the number of events will be evaluated PPPY in baseline and follow-up. See covariate definition above for operational definition and Table 5 for output definition.
ACS Including Pneumonia	For each patient, the number of events will be evaluated PPPY in baseline and follow-up. See covariate definition above for operational definition and Table 5 for output definition.
Priapism	For each patient, the number of events will be evaluated PPPY in baseline and follow-up. See covariate definition above for operational definition and Table 5 for output definition.
Iron overload	For each patient, iron overload will be evaluated as the time to event in days. See covariate definition above for operational definition and Table 5 for output definition.
Iron chelation use	For each patient, iron chelation will be evaluated as the time to event in days. See covariate definition above for operational definition and Table 5 for output definition.
Delayed hemolytic transfusion reactions Alloimmunization	For each patient, DHTR will be evaluated as the time to event in days. See covariate definition above for operational definition and Table 5 for output definition.
Composite outcome (iron overload, iron chelation use, Delayed hemolytic transfusion reactions, and/or alloimmunization)	For each patient, the composite outcome will be evaluated as the time to event (the first of any) in days. See covariate definition above for operational definition and Table 5 for output definition.

Diagnosis (ICD), procedure (ICD, CPT, HCPCS), and drug codes (NDC) or generic names will be documented in the code list accompanying the statistical analysis plan.

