Iron chelation use	Baseline Characteristic; Covariate	[Baseline]	Frequency and proportion (N, %)
Delayed hemolytic transfusion reactions	Baseline Characteristic; Covariate	[Baseline]	Frequency and proportion (N, %)
Alloimmunization	Baseline Characteristic; Covariate	[Baseline]	Frequency and proportion (N, %)
Death	Baseline Characteristic; Covariate	[Follow-up]	Frequency and proportion (N, %)
Voxelotor discontinuation	Baseline Characteristic; Covariate	[Follow-up]	Frequency and proportion (N, %)

Abbreviations: ESA: Erythropoietin Stimulating Agent; RBC: Red blood cell; SCD: Sickle cell disease.

Baseline genotype will not be included in the PS model because patients commonly have multiple values due to coding/billing errors and this value is more likely to be misclassified. The most frequently occurring value (not including unknown/other) will be selected

- 2. SCD-specific comorbidities include the following: acute chest syndrome, acute coronary syndrome, acute osteomyelitis, acute renal failure, aplastic crisis, intracerebral and subarachnoid hemorrhage, myocardial infarction, priapism, splenic sequestration crisis, transfusion-associated reaction, venous thromboembolism, avascular necrosis, cholelithiasis, chronic kidney disease, chronic pain, diabetes, heart failure, iron overload, leg ulcer, pulmonary hypertension, VOC, and retinopathy.
- 6. Given feasibility analyses have indicated a low proportion of patients (<25%) have lab values, Hb will be excluded from the PS model. Hb will be evaluated excluding those measurements within 2 days of an acute event or within 30-60 days of a transfusion event. Full algorithm will be provided in a separate statistical analysis plan.
- 4. CCI categories include: myocardial infarction, congestive heart failure, peripheral vascular disease, cerebrovascular disease, dementia, chronic pulmonary disease, rheumatic disease, peptic ulcer disease, mild liver disease, diabetes without chronic complication, diabetes with chronic complication, hemiplegia or paraplegia, renal disease (mild to moderate), renal disease (severe), any malignancy without metastasis including leukemia and lymphoma, moderate or severe liver disease, metastatic solid tumor, human immunodeficiency virus, acquired immunodeficiency syndrome

The table above includes a summary of baseline characteristics and possible covariates for PS modeling. Covariates will be selected using the diagnostic criteria outlined in the data analysis plan (Section 9.7).

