Table 5. Description of Endpoints and Alignment to Study Objectives

Endpoint	Assessment Period	Output	Objective Alignment
Change in RBC transfusions	[Baseline]; [Follow-up]	Mean change in the number of RBC transfusions (maximum 1 per day) PPPY from baseline to follow-up	Primary Objective
VOCs	[Baseline]; [Follow-up]	Mean change in the number of events (maximum 1 per day) PPPY from baseline to follow-up. VOC events need to occur more than 5 days apart to be considered separate events.	Exploratory Objective 1.1
ACS	[Baseline]; [Follow-up]	Mean change in the number of events (maximum 1 per day) PPPY from baseline to follow-up	Exploratory Objective 1.1
ACS Including Pneumonia	[Baseline]; [Follow-up]	Mean change in the number of events (maximum 1 per day) PPPY from baseline to follow-up	Exploratory Objective 1.1
Priapism	[Baseline]; [Follow-up]	Mean change in the number of events (maximum 1 per day) PPPY from baseline to follow-up	Exploratory Objective 1.1

Voxelotor

V2.0 23 December 2024		9	
Stroke (including transient ischemic attack)	[Follow-up]	Time to event during follow-up	Exploratory Objective 1.2
RBC transfusions in follow-up	[Follow-up]	Mean number of RBC transfusions (maximum 1 per day) PPPY in follow-up	Exploratory Objective 2
Percent reduction in RBC transfusion > 30%	[Baseline]; [Follow-up]	Proportion of patients with a percentage decrease in the number of RBC transfusions (maximum 1 per day) PPPY from baseline to follow-up that is greater than 30%	Exploratory Objective 2
Zero RBC transfusions in follow-up	[Follow-up]	Proportion of patients with 0 RBC transfusions (maximum 1 per day) PPPY during follow- up	Exploratory Objective 2
Iron overload	[Follow-up]	Time to event during follow-up	Exploratory Objective 3
Iron chelation use	[Follow-up]	Time to event during follow-up	Exploratory Objective 3
Delayed hemolytic transfusion reactions	[Follow-up]	Time to event during follow-up	Exploratory Objective 3
Alloimmunization	[Follow-up]	Time to event during follow-up	Exploratory Objective 3
Composite outcome (iron overload, iron chelation use, delayed hemolytic transfusion reactions, and/or alloimmunization)	[Follow-up]	Time to event during follow-up	Exploratory Objective 3

Abbreviations: ACS: Acute Chest Syndrome; PPPY: per patient per year; RBC: Red blood cell; VOC: vaso-occlusive crisis The table above includes a summary of the outcomes of interest for this analysis. Operational definitions can be found in the data analysis plan (Section 9.7).

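### The primary (strict) VOC code list mixes code levels, so no matching rule applies one VOC definition across its six code families

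*Protocol*

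**What the plan says.** Annex Table 1 gives two VOC definitions. The first is labelled "Definition 1 (primary analysis, strict definition" and reads "Presence of ICD-10 diagnoses code for SCD with VOC (D57.09, D57.21, D57.41, D57.43, D57.45, D57.81) or dactylitis (D57.04, D57.214, D57.414, D57.434, D57.454, D57.814", on an urgent care, emergency or inpatient claim. The second, for sensitivity analysis, takes the first definition "and/or VOC component (e.g., ACS, priapism, stroke, splenic sequestration, or crisis unspecified" and adds telemedicine, office and outpatient settings. The entry closes with "Final definition to be included in SAP". The protocol does not say whether codes are matched exactly or as prefixes.

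The definition is used in two places. VOC is an endpoint of exploratory objective 1.1, analysed in Section 9.7.3 as the within-patient change in annualised event rate. VOC is also one of the SCD-specific comorbidities in the footnotes to Table 4, which makes it a candidate propensity score covariate. The outcome row for VOC in Annex Table 1 refers back to the covariate definition.

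Table 5 (Section 9.3) sets the counting rule: at most one event per day, and "VOC events need to occur more than 5 days apart to be considered separate events". On adjustment, the footnotes to Table 4 state: "Baseline genotype will not be included in the PS model".

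**The concern.** A code list meant to capture one clinical event across several code families should enter every family at the same level of the hierarchy. Otherwise the definition itself makes the share of true VOCs that is captured depend on which family a patient's claims use. Genotype is kept out of the propensity score model, so nothing in the primary adjustment is aimed at balancing a characteristic that may track the code family. The sensitivity analysis by genotype mentioned in Annex Table 3 concerns RBC transfusion, not VOC.

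The stake is the VOC comparison. It is exploratory, but a substantial amendment restored it, and Section 9.1 treats the absence of clinical worsening as a key consideration when interpreting fewer transfusions. Baseline VOC status as a confounder is a smaller, second stake.

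**Working it through.** **Inputs.** The twelve codes in Definition 1, the Table 5 gap rule, and the change formula in Section 9.7.3. The plan states no figure on this point, so there is none to reproduce.

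**Step 1: structure of the list.** For each dactylitis code, ask whether it begins with a listed crisis code.

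| Crisis code | Dactylitis code | Dactylitis extends crisis code? |
|---|---|---|
| D57.09 | D57.04 | No: siblings under D57.0 (not listed) |
| D57.21 | D57.214 | Yes |
| D57.41 | D57.414 | Yes |
| D57.43 | D57.434 | Yes |
| D57.45 | D57.454 | Yes |
| D57.81 | D57.814 | Yes |

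One family is entered at child level and five at parent level.

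**Step 2: the two matching rules.**

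- *Prefix.* Each of the five parents takes in all its sub-codes. Their five dactylitis entries are then redundant. The first family counts D57.09 and D57.04 only.
- *Exact.* Each family has two codes, which looks parallel but is not. In the first family the crisis code is a sibling of the dactylitis code. In the other five it is the bare parent, and every sub-code other than dactylitis is missed.

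Listing dactylitis separately suggests that exact matching was intended, but the text does not say so. Under neither rule is the first family treated like the other five.

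**Step 3: effect on a change score.** Let c be the share of true VOCs captured in a family, assumed the same in baseline and follow-up, and let D be the true change in annual rate. The observed change is c × D. Subtracting baseline therefore does not remove c, but if D = 0 the observed change is 0 whatever c is.

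Take two groups of families with capture c1 and c2, and suppose the true change D is the same in both arms (no treatment effect). Let wT and wC be the shares of treated and control patients in the first group. The observed arm difference is

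[c1·wT + c2·(1 − wT)]·D − [c1·wC + c2·(1 − wC)]·D = (c1 − c2)·(wT − wC)·D.

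A spurious difference needs all three factors to be non-zero: unequal capture, unequal family mix, and a change in rates. With equal mix and a real effect, the effect is scaled by the average capture. If effects differ by family, they are also reweighted. The documents give none of c1, c2, wT, wC or D, so no size can be computed.

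**Step 4: the five-day gap.** Events counted for one continuous admission, by reading of Table 5:

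| Reading | Up to 6 days | 7–12 days | 13–14 days | 21 days |
|---|---|---|---|---|
| Daily claims, gap from the last counted event | 1 | 2 | 3 | 4 |
| Daily claims, gap from the most recent claim | 1 | 1 | 1 | 1 |
| One dated claim per stay | 1 | 1 | 1 | 1 |

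Only the first of these splits a stay. If claims within a stay were themselves more than five days apart (for example only on the first and last day of a stay of 7 days or more), the second rule would also give two. Table 5 does not say which reading applies.

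**The case against.** The strongest reply is deferral. Annex Table 1 leaves the code lists and the final VOC definition to the SAP, which is not among the documents at hand, and Section 9.3 requires all codes to be reviewed. On that view the list is provisional. This stands as a limit on how firmly the point can be put: it is a stated rule to correct, not a demonstrated miscount in results. It does not dispose of the point, because the protocol prints a specific list and labels it primary. Section 9.8.1 also says that measures are built from the codes and algorithms in the protocol and that the protocol will be strictly followed.

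A second reply is that Section 9.9 admits VOC misclassification and plans a broader algorithm. That helps only in part. Definition 2 contains Definition 1 and so inherits its list. It also widens codes and care settings together, so comparing the two definitions would not isolate the level problem.

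A third reply, that within-patient change removes the problem, is right only when rates do not change (Step 3).

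A reader might go further than the documents allow in three ways:

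- *That VOCs are shown to be counted unequally by genotype, by a known amount.* The protocol does not label the codes by genotype (Table 4 names four genotypes, while the list has six families). It does not show what the other sub-codes contain or whether parent codes appear on claims, and it gives no code frequencies.
- *That any genotype difference between arms becomes a VOC difference.* It does so only together with unequal capture and a non-zero change in rates.
- *That one long admission counts as several VOCs.* This depends on a gap anchor and a claim pattern that Table 5 does not state. An admission that crosses index is likewise unresolved rather than shown to be double counted. Both are SAP-level details.

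**Conclusion.** The point holds as a defect in the stated rule. Definition 1 enters one family at child level and five at parent level, and neither prefix nor exact matching applies one VOC definition to all six. This follows from the printed code strings and needs no outside source.

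Its consequence is conditional. The exploratory VOC comparison can be distorted if capture differs by family, the family mix differs between arms, and VOC rates change from baseline. Excluding genotype from the propensity score model leaves room for the second condition. Neither direction nor size can be derived from the documents. The primary endpoint counts transfusions and does not use this list. The only route to it is baseline VOC as a candidate propensity score covariate.

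The anchor of the five-day gap and the dating of inpatient stays are details for the SAP to state, not a shown counting error.

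**What to change.** In Definition 1, list the parallel child-level codes for all six families and state that matching is exact. Keep the component and unspecified-crisis codes in Definition 2 unless they are deliberately included in Definition 1 for every family. Entering all six parents as prefixes would also put the families on one level, but it could bring Definition 2 content into the strict definition, so it should not be done as a mere wording change.

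Carry the same list into the SAP and into the baseline VOC covariate. In the SAP, state where the five-day gap is measured from, how an inpatient stay is dated, and to which period a stay that crosses index belongs.

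The cost is code-list wording before outcome programming. No new data are needed. VOC counts may change, and baseline VOC balance should be checked with the corrected list before the propensity score model is fixed.
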